4.2.2 Phase II Design

Subjects in the Phase II/Run-in period will receive an initial cycle with carfilzomib at the twice weekly dose of 56mg/m² and dexamethasone. Following Cycle 1, a response assessment will be done. Subjects with a response of PR or better (“Responders”) will continue therapy with carfilzomib and dexamethasone. After these responding subjects subsequently progress, they will be treated with ruxolitinib (at the dose established in Phase 1) in combination with carfilzomib and dexamethasone. Subjects with a response of less than PR (“Non-responders”) will add ruxolitinib at the dose established in Phase I to carfilzomib and dexamethasone for all subsequent cycles. The cycle when ruxolitinib is added will be considered Cycle 1 (cycle numbers will start over). Disease evaluation assessment results should be available prior to dosing on Day 1 of each cycle of Phase II until initiation of ruxolitinib treatment (to ensure initiation of ruxolitinib occurs on Day 1 of a cycle).

Enrollment in the Phase II part of the study will be carried out in two stages. During the first stage, 10 PFS evaluable subjects (Section 13.3) will be enrolled. Enrollment and Stage 1 analysis of the first ten subjects on the three drugs (carfilzomib-ruxolitinib-dexamethasone) will be completed to determine if at least 3 of 10 subjects are alive and progression free at 4 months. If so, an additional 20 subjects will be enrolled (a total of 30 subjects) during the second stage. If at least 11 of 30 subjects are alive and progression free at 4 months, the null hypothesis will be rejected (based on binomial probabilities, see Section 13.1.2). The overall duration of the Phase II portion of the study is expected to be no longer than 24 months. For both Phase I and Phase II, subjects will be assessed for response after each cycle with confirmation of response according to IMWG response criteria regardless of dose level treated. Doses of each study drug may be interrupted or reduced in an attempt to manage toxicity.

Table 2: Phase II/Run-In Dosing^a

Drug	Dose	Route	Schedule	Cycle Length
------	------	-------	----------	--------------

Dexamethasone	40 mg ^b	PO	D1, 8, and 15 (Prior to carfilzomib)	28 days
Carfilzomib	56 mg/m ^{2c}	Intravenously (IV) over 30 minutes	D1, 2, 8, 9, 15, and 16	

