4.3 Subject Enrollment

Phase I

Enrolled subjects in Phase I will be DLT evaluable if they experience a DLT during Cycle 1 of treatment with the carfilzomib, ruxolitinib and dexamethasone regimen.

Enrolled subjects in Phase I who do **not** experience a DLT must meet all of the criteria below to be DLT evaluable:

- complete Cycle 1 of ruxolitinib therapy defined as followed
 - initiate Cycle 2, or
 - discontinue ruxolitinib therapy prior to Cycle 2 if the discontinuation date (as defined in Section 4.1) is on Cycle 1 Day 25 or later
- return no more than 20% of the number of ruxolitinib pills prescribed for Cycle 1 (while taking into account the actual length of Cycle 1)
- do not receive G-CSF or platelet transfusions during Cycle 1

Subjects who discontinue study treatment without experiencing a DLT and do not meet the DLT criteria as stated above will not be included in the 3+3 MTD evaluation but will be included in the overall analyses. Enrollment of new subjects to the current cohort will only be considered if there is less than the required number of DLT evaluable subjects to determine toxicity for the cohort. For example, of 3 subjects in a cohort, one withdraws due to disease progression, but 2 others have DLT, there is no need to continue enrollment to the given cohort as the MTD has already been exceeded. Alternatively, of 3 subjects in a cohort, one withdraws due to disease progression, but 2 others have not experienced a DLT, enrollment to the cohort will continue to fully evaluate the cohort with three DLT evaluable subjects).

Phase II

All enrolled subjects will remain in the intent to treat population. Enrollment to the Phase II part of the study will continue until the sample size requirements for the PFS4 evaluable population are achieved (Section 13.3).

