13.1.2 Phase II

Progression-free survival at 4 months is the primary endpoint for this study. The current study is investigating the impact of adding ruxolitinib to the combination of carfilzomib and dexamethasone in a carfilzomib refractory population. Published study results on carfilzomib plus dexamethasone in a carfilzomib refractory population (as defined in this protocol) have not

been identified. However, it is reported that the time on treatment in multiple myeloma patients receiving three or more lines of therapy had a median time on treatment of approximately 2 months²⁹. Therefore, it is assumed that if multiple myeloma subjects who are carfilzomib-refractory were retreated with carfilzomib plus low-dose dexamethasone, they would experience a median PFS of 2 months. A 2-month median PFS corresponds to a 4-month progression-free survival rate of 25%. In this patient population, if subjects treated with carfilzomib, ruxolitinib, and low-dose dexamethasone achieved a median PFS of 4 months, this would be considered a significant clinical benefit. A 4-month median PFS corresponds to a 4-month progression-free survival rate of 50%. A Simon's 2-stage design will be used to test the hypothesis that the 4-month PFS rate is less than or equal to 25%. Ten subjects will be enrolled in the first stage, and if at least 3 of the 10 subjects are alive and progression free at 4 months, an additional 20 subjects will be enrolled (a total of 30 subjects). If at least 11 of 30 subjects are alive and progression free at 4 months, the null hypothesis will be rejected (based on binomial probabilities). Assuming a one-sided alpha = 0.10 significance level, this sample size will provide at least 90% power to reject the null hypothesis, assuming the true 4-month PFS rate is 50%.

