13.3 Analysis Populations

For the Phase I part of the study, the dose escalation and MTD evaluation will be conducted on the population who initiate Cycle 1, Day 1 treatment, and who meet the DLT evaluable criteria as described in Section 4.3. For the Phase II part of the study, the PFS4 evaluable population will include all subjects who initiate treatment with ruxolitinib, have experienced a PFS event within 4 months from the start of ruxolitinib treatment, or have at least 4 months of follow up time from the start of ruxolitinib treatment. The primary efficacy analysis will be conducted on the PFS4 evaluable population. Response-evaluable population will include all subjects (both Phase I and Phase II) who have baseline evaluation, measurable disease, and initiate study

treatment followed by at least one efficacy measurement. All response endpoints will be conducted on the response-evaluable population.

All other efficacy and ruxolitinib safety analyses will be conducted on the population of subjects (both Phase I and Phase II) who initiate treatment with ruxolitinib. Additionally, an analysis will be conducted on safety data collected from Cycle 1 through the cycle prior to initiation of ruxolitinib treatment (for all Phase II subjects initiating Cycle 1 with carfilzomib plus dexamethasone).

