13.4 Analysis Methods

13.4.1 Timing of Analyses

For the Phase I part of the study, an evaluation of the data will take place after each subject completes Cycle 1. For the Phase II part of the study, AESIs will be continuously evaluated in order to assess the Bayesian stopping rules for toxicity described in Section 13.4.3. Additionally, the stage 1 analysis will occur after the first 10 PFS evaluable subjects enrolled have progressive disease, have died, or have at least 4 months of follow up time from ruxolitinib treatment start. The stage 2 analysis will occur after 30 PFS evaluable subjects have progressive disease, have died, or have at least 4 months of follow up time. For both Phase I and Phase II, a follow up analysis will occur when all enrolled subjects have progressed, have died, have become lost to follow up or withdrawn from the study, or have at least two years of follow up time after initiation of treatment with ruxolitinib. A final analysis (for both Phase I and Phase II) will occur when all subjects have died, have become lost to follow up or withdrawn from the study, or have at least 3 years of follow up time after initiation of treatment with ruxolitinib.

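### The Phase II rules allow the 30 primary-analysis subjects to be the first 30 to become PFS4 evaluable, which favours failures; the stated 90% power holds only if the set is fixed without regard to outcome

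*Combined protocol and SAP*

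**What the plan says.** Section 13.3 admits a subject who starts ruxolitinib to the PFS4 evaluable population if they "have experienced a PFS event within 4 months from the start of ruxolitinib treatment, or have at least 4 months of follow up time", and bases the primary efficacy analysis on that population. Section 4.3 ties the end of accrual to the same count: "Enrollment to the Phase II part of the study will continue until the sample size requirements for the PFS4 evaluable population are achieved". Section 13.4.1 times the final analysis likewise: "The stage 2 analysis will occur after 30 PFS evaluable subjects have progressive disease, have died", or have 4 months of follow-up.

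Stage 1 is described in three ways. Section 4.2.2 has "Enrollment and Stage 1 analysis of the first ten subjects on the three drugs". Section 13.4.1 refers to the first 10 evaluable subjects enrolled. Section 13.5 suspends accrual once 10 evaluable subjects are enrolled and times the interim from the tenth subject's enrolment.

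Section 13.1.2 sets the rule (continue at 3 or more of 10, reject at 11 or more of 30) and states its performance: "Assuming a one-sided alpha = 0.10 significance level, this sample size will provide at least 90% power to reject the null hypothesis", for a true 4-month rate of 50% against a null of 25%.

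**The concern.** Failures and successes reach evaluable status at different speeds. Suppose one subject starts ruxolitinib at month 8 and stays event-free, and another starts at month 10 and progresses at month 11. The second is evaluable at month 11 and the first at month 12, so the later starter with the worse outcome enters first. When the 30th subject becomes evaluable, every treated subject still in follow-up outside the set is event-free, since an event would already have admitted them.

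The 11-of-30 boundary assumes subjects chosen without regard to outcome. If the set fills in order of evaluability, the PFS4 estimate is biased downward, power is lost, and some treated subjects never enter the primary test. The text does not say which 30 are analysed, what happens to pending subjects, or what boundary applies if more than 30 are evaluable.

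**Working it through.** **Inputs.** From 13.1.2: null rate 0.25, alternative 0.50, rule 3/10 then 11/30, one-sided alpha 0.10, power at least 90%. Under exponential PFS the rates follow from the medians as S(4) = 0.5^(4/median): 0.5^2 = 0.25 and 0.5^1 = 0.50. Accrual pace is not stated. From the 24-month Phase II duration in 4.2.2, 30/24 = 1.25 per month, 30/20 = 1.5 after removing a 4-month pause, and 30/16 = 1.9 after also removing the last 4-month follow-up. I use 1 to 3 ruxolitinib starts per month as an assumed range.

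**1. The plan's own figure.** Reject probability = sum over x = 3..10 of b(x; 10, p) × P(Bin(20, p) ≥ 11 − x).

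- p = 0.50: 0.1172×0.8684 + 0.2051×0.9423 + 0.2461×0.9793 + 0.2051×0.9941 + 0.1172×0.9987 + 0.0439×0.9998 + 0.0098 + 0.0010 = **0.912**.
- p = 0.25: the same sum gives **0.091**.

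The design is sound for a set fixed without regard to outcome.

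**2. Subjects left out if Stage 2 fills by evaluability (true rate 0.50).** The mean time a subject is treated but not yet evaluable is E[min(T, 4)] = (1 − 0.5)/(ln 2/4) = 2.885 months. At 2 starts per month, 2 × 2.885 = 5.8 event-free subjects are pending when the last place fills.

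**3. Bias in the estimate.** Of those 5.8, 2 × 4 × 0.5 = 4.0 will reach 4 months event-free. Expected successes among the 20 Stage 2 places are therefore (20 + 5.77) × 0.5 − 4.0 = 8.9 instead of 10. Among trials that pass Stage 1, the mean Stage 1 count is 0.506 × 30 − 10 = 5.19. Mean PFS4 is (5.19 + 8.89)/30 = 0.47, against 0.506 for a fixed set.

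**4. Power and type I error.** Simulation with 40,000 trials per setting, exponential PFS and Poisson starts. Stage 1 is in order with the accrual pause; Stage 2 is the next 20 to become evaluable; nobody is lost.

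| Starts per month | Power at 50% | Power if progression is found only at 28-day visits | Type I error at 25% | Left out at trigger (50%) |
|---|---|---|---|---|
| Fixed set | 0.912 | 0.912 | 0.091 | 0 |
| 1 | 0.892 | 0.897 | 0.065 | 2.9 |
| 1.25 | 0.886 | 0.894 | 0.058 | 3.6 |
| 1.5 | 0.880 | 0.886 | 0.055 | 4.3 |
| 2 | 0.864 | 0.876 | 0.043 | 5.8 |
| 3 | 0.828 | 0.852 | 0.028 | 8.7 |

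Other runs under the same assumptions differ by up to about 0.01.

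**5. The alternative reading.** If everyone treated when the 30th becomes evaluable is followed to 4 months and analysed, the failure-first selection disappears. About 30 + 4.3 = 34 subjects (1.5 per month) to 30 + 5.8 = 36 (2 per month) then enter, and the 11-of-30 rule does not cover that number.

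**The case against.** The strongest reply is that the plan means a cohort in enrolment order. Section 4.2.2 names the first ten on the three drugs and then adds 20 for a total of 30. Section 13.4.1 refers to the first 10 enrolled, and 13.5 pauses accrual until the tenth has an outcome. The Stage 2 wording also waits for evaluable subjects to have an outcome, which would be redundant if evaluable already meant that the outcome is known. On that reading the stated power reproduces.

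Much of this stands for Stage 1. A reader might infer that both stages fill failure-first, which would put power at about 0.83 at 1.25 starts per month, 0.81 at 1.5 and 0.77 at 1.9. The documents do not support that as the natural case, because all three Stage 1 descriptions can be read as a set in order, with a pause.

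The reply is weaker for Stage 2, whose trigger has neither the word first nor the word enrolled, and 4.3 stops accrual on the evaluable count. Nor is enrolment order a complete answer. Phase II enrolment is dated from the first study treatment, with or without ruxolitinib (4.1), while the PFS4 clock starts at ruxolitinib (13.2.2). Run-in responders start ruxolitinib only after later progression, so the two orders differ.

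It is also fair to say that 13.3 includes all subjects meeting its definition, so exclusion of pending subjects is not certain, and that Kaplan-Meier PFS uses everyone who starts ruxolitinib. The first point leads to the missing boundary. The second does not alter the primary binomial test.

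**Conclusion.** The point holds as a conditional one and is worth correcting. As written, the accrual, population and timing rules permit a final set selected partly on outcome. The claim of at least 90% power holds only if the 10 and the 30 are fixed without regard to outcome. If Stage 2 alone fills by evaluability, power at a true rate of 50% is about 1 to 4 points below 90% at 1 to 2 ruxolitinib starts per month, and 7 to 8 points below at 3. The loss is somewhat smaller with progression found only at 28-day visits. These sizes rest on an assumed accrual pace, exponential PFS and no loss to follow-up.

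Two stronger inferences are not supported. The trial is not bound to miss its power, because failure-first filling is one reading of the text. There is no added false-positive risk either: type I error falls, from 0.091 to between about 0.03 and 0.065. What is at stake is a missed signal from an active combination and a PFS4 estimate biased downward.

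**What to change.** In 4.3, 13.3, 13.4.1 and 13.5, define Stage 1 and Stage 2 as the first 10 and first 30 Phase II subjects by date of first ruxolitinib dose, and align 4.2.2 with this. Close accrual on the count of ruxolitinib starts. Analyse when every subject in the set has an event, has 4-month status, or has been lost before 4 months. Report later starters, including anyone still in the run-in when the thirtieth place is taken, separately and outside the 11-of-30 rule.

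State how subjects lost early are scored: for example, counted as not progression-free, with the Kaplan-Meier 4-month rate as a sensitivity analysis.

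The change is wording in a few sections and adds no patients. With no loss, it restores power to 0.912. Its price is that subjects lost early are no longer replaced. If they count as failures, 5% loss by month 4 (independent of progression) gives a success rate of 0.50 × 0.95 = 0.475, and the formula in step 1 then gives power 0.869; 10% loss gives 0.45 and 0.811. Excluding and replacing them in start order gives 0.901 and 0.888, but replaces only event-free subjects and never failures. The expected loss rate should therefore be stated when the scoring rule is chosen.

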5 STUDY TREATMENT

Treatment will be administered on an outpatient basis. Reported adverse events and potential risks are described in the Investigational Brochure and Prescribing Information. Appropriate dose modifications are described in Section 6.

The study drugs must be exclusively used for the investigation specified in this protocol and will only be accessible to authorized staff.

5.1 Carfilzomib

5.1.1 Carfilzomib Dose

Subjects will receive carfilzomib 56 mg/m²/day IV over 30 minutes on Days 1, 2, 8, 9, 15 and 16 of a 28-day cycle. Subjects who have received CFZ < 56mg/m² more than 60 days prior to informed consent should receive CFZ 20mg/m² on Days 1 and 2 of the first cycle of carfilzomib with subsequent doses of 56mg/m².

The dose will be calculated using the subject's actual BSA at baseline. Subjects with a BSA > 2.2 m² will receive a dose based upon a 2.2 m² BSA. Dose adjustments do not need to be made for weight changes of less than or equal to 20% from baseline weight.

5.1.2 Carfilzomib Administration

5.1.2.1 Hydration and Fluid Monitoring

- At least 48 hours before the first dose of carfilzomib, oral hydration should be given as follows: 30 mL/kg/day (approximately 6 to 8 cups of liquid per day) continuing up to the time of treatment. Subject compliance must be assessed before initiating treatment, which is to be delayed if oral hydration is not adequate. In subjects considered at risk for TLS, oral hydration should be continued in Cycle 2 and beyond as required by the subject's medical condition and at the Investigator's discretion.
- IV hydration will be given immediately prior to carfilzomib during the first cycle of carfilzomib. This will consist of 250 to 500 mL normal saline or other appropriate IV fluid. Co-morbidities should be considered when determining the appropriate volume of fluid to administer (e.g. consider 250 ml for subjects with increased cardiac risk). If lactate dehydrogenase (LDH) or uric acid is elevated (and/or in subjects considered still at risk for TLS) at the completion of the first cycle of carfilzomib (Cycle 2 Day 1), then the recommended IV hydration should be given additionally before each dose in the second cycle. The goal of the hydration program is to maintain robust urine output (e.g. ≥ 2 L/day). Subjects should be monitored periodically during this period for evidence of fluid overload.

- If the subject has a dedicated line for carfilzomib administration, the line must be flushed with a minimum of 20 mL of normal saline prior to and after drug administration.

5.1.2.2 Carfilzomib Infusion

- Carfilzomib will be given as an IV infusion over approximately 30 minutes. The dose will be administered at a facility capable of managing hypersensitivity reactions. Subjects will remain at the clinic under observation for at least 1 hour following each dose of carfilzomib in the first cycle of carfilzomib. During these observation times, post dose IV hydration (between 250 mL and 500 mL normal saline or other appropriate IV fluid formulation) is recommended but will be administered per the investigator's discretion. Subjects should be monitored periodically during this period for evidence of fluid overload.

5.1.3 SAFETY CONSIDERATIONS

- A “first dose effect” has been seen, which is notable for fever, chills, rigors, and/or dyspnea occurring during the evening following the first day of infusion and an increase in creatinine on Day 2, which may be the clinical sequelae of rapid tumor lysis and/or cytokine release.
- Should a “first dose” effect occur at any point during the first or second cycle of carfilzomib, treatment with high dose glucocorticoids (e.g. methylprednisolone 50–100 mg) is recommended. In addition, intravenous fluids, vasopressors, oxygen, bronchodilators, and acetaminophen should be available and instituted, as medically indicated.
- Acyclovir or similar should be given to all subjects, per institutional prophylaxis guidelines, unless contraindicated.
- For subjects who are carriers of HBV, prophylaxis with antivirals should be considered.
- CrCl changes are mostly transient, reversible, and non-cumulative. All subjects should be well hydrated. Clinically significant electrolyte abnormalities should be corrected prior to dosing with carfilzomib. Renal function must be monitored closely during treatment with carfilzomib. Serum chemistry values, including creatinine, must be obtained and reviewed prior to each dose of carfilzomib on Day 1, 8, and 15 of all cycles. Carfilzomib must be held for subjects with a CrCl < 15 mL/min at any time during study participation as outlined in Section [6.3](#).
- Subjects with active or suspected infection of any kind that required IV systemic treatment should not be dosed with carfilzomib until the infection has resolved and if being treated with anti-infective, the course of antibiotics has been completed.
- Thrombocytopenia has been transient and typically resolves during the week between treatments. For platelet counts $\leq 25,000/\text{mm}^3$, carfilzomib dosing must be held. If

platelet counts do not recover, the dose of carfilzomib may be reduced or held according to the Dose Reductions / Adjustments rules outlined in Section [6.3](#).

- Subjects should have anemia treated in accordance with the Institutional guidelines.
- Carfilzomib treatment can cause nausea, vomiting, diarrhea, or constipation sometimes requiring the use of antiemetics or antidiarrheals. Fluid and electrolyte replacement should be administered as clinically indicated to prevent dehydration.
- Subjects with a history of HBV should be closely monitored for signs and symptoms of active HBV infection throughout treatment with carfilzomib, including the 30-day safety monitoring follow-up period.
- Subjects receiving carfilzomib should be monitored for any new or worsening neurologic, cognitive or behavioral signs and symptoms that may be suggestive of Progressive Multifocal Leukoencephalopathy (PML) as part of the differential diagnosis of central nervous system disorders. If PML is suspected, subjects should be referred to a specialist and appropriate diagnostic testing should be initiated. If a PML diagnosis is confirmed, carfilzomib should be permanently discontinued.
- Contraception/Female: Females of childbearing potential should be advised to avoid becoming pregnant while being treated with carfilzomib. Given that carfilzomib was clastogenic in the in vitro chromosomal aberration test in peripheral blood lymphocytes, as a precaution, females of childbearing potential and/or their male partners should use effective contraception methods or abstain from sexual activity during and for 30 days after treatment with carfilzomib. If pregnancy occurs during this time, patients should be apprised of the potential hazard to the fetus.

Based on its mechanism of action and findings in animals, carfilzomib can cause fetal harm when administered to a pregnant woman. Carfilzomib caused embryo-fetal toxicity in pregnant rabbits at doses that were lower than in subjects receiving the recommended dose. Carfilzomib administered to pregnant rats and rabbits during the period of organogenesis was not teratogenic at doses up to 2 mg/kg/day in rats or up to 0.8 mg/kg/day in rabbits. If carfilzomib is used during pregnancy, or if the subject becomes pregnant while taking this drug, she should inform the investigator or study staff immediately. The investigator should notify Amgen of the pregnancy and discuss follow-up with the subject. It is not known if carfilzomib will reduce the efficacy of oral contraceptives. Due to an increased risk of venous thrombosis associated with carfilzomib, subjects currently using oral contraceptives, or a hormonal method of contraception associated with a risk of thrombosis should consider an alternative method of effective contraception.

- Breastfeeding: No studies of carfilzomib have been conducted in breastfeeding women. Carfilzomib should not be used during breastfeeding. Breastfeeding women and women planning on breastfeeding may not participate in clinical trials with carfilzomib.

If a woman breastfeeds during the study, she must inform the investigator or study staff immediately. The investigator should notify Amgen that the subject has breastfed the infant and discuss follow-up with the subject.

- **Contraception/Male:** Males of reproductive potential should be advised to avoid fathering a child while being treated with carfilzomib. The potential for carfilzomib to be transferred via semen and its effect on sperm are unknown. Male subjects should refrain from donating sperm for at least 90 days after the last dose of carfilzomib. Male subjects treated with carfilzomib and/or their female partners (if of childbearing potential) should use effective contraceptive methods or abstain from sexual activity while treated with carfilzomib and for 90 days after treatment. If pregnancy occurs during this time, patients should be apprised of the potential hazard to the fetus.

Male subjects should be advised to inform the investigator or study staff immediately in the event that their female partner becomes pregnant during the study. Upon receipt of this information, the investigator should notify Amgen of the pregnancy and discuss follow-up regarding the pregnancy outcome with the subject.

